7.1.4.2 Evaluation of Non-Target Lesions (para-aortic/ pelvic nodes)

Complete Response (CR): Disappearance of all non-target lesions.

Incomplete Response/Stable Disease (SD): Persistence of one or more non-target lesion(s) and/or maintenance of tumor marker level above the normal limits.

Progressive Disease (PD): Appearance of one or more new lesions and/or unequivocal progression of existing non-target lesions

7.1.4.3 Evaluation of Best Overall Response

The best overall response is the best response recorded from the start of the treatment until disease progression/recurrence (taking as reference for progressive disease the smallest measurements recorded since the treatment started). The patient's best response assignment will depend on the achievement of both measurement and confirmation criteria.

Target Lesions	Non-Target Lesions	New Lesions	Overall Response	Best Response for this Category Also Requires:
CR	CR	No	CR	≥ 4 wks. confirmation
CR	Non-CR/Non-PD	No	PR	≥ 4 wks. confirmation
PR	Non-PD	No	PR	
SD	Non-PD	No	SD	Documented at least once ≥ 4 wks. from baseline
PD	Any	Yes or No	PD	no prior SD, PR or CR
Any	PD*	Yes or No	PD	
Any	Any	Yes	PD	

* In exceptional circumstances, unequivocal progression in non-target lesions may be accepted as disease progression.
 
Note: Patients with a global deterioration of health status requiring discontinuation of treatment without objective evidence of disease progression at that time should be reported as “symptomatic deterioration”. Every effort should be made to document the objective progression even after discontinuation of treatment.
				

Note: If subjects respond to treatment and are able to have their disease resected, the patient's response will be assessed prior to the surgery.

7.1.5 Duration of Response

Duration of overall response: The duration of overall response is measured from the time measurement criteria are met for CR or PR (whichever is first recorded) until the first date that recurrent or progressive disease is objectively documented (taking as reference for progressive disease the smallest measurements recorded since the treatment started).

The duration of overall CR is measured from the time measurement criteria are first met for CR until the first date that recurrent disease is objectively documented.

Duration of stable disease: Stable disease is measured from the start of the treatment until the criteria for progression are met, taking as reference the smallest measurements recorded since the treatment started.

7.1.6 Progression-Free Survival

Progression-free survival (PFS) is defined as the duration of time from start of treatment to time of progression.

This will be further differentiated as Local tumor (cervix-which is primary endpoint) , Regional(pelvic nodal) and distant (Paraortic and visceral organ)metastases.

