1. BACKGROUND AND RATIONALE

1.1 Disease Background

Locally Advanced Cervical Cancer (LACC)

There will be an estimated 12,300 new cases of cervical cancer diagnosed in the United States in 2013, with one third that number dying from the cancer [1]. While the incidence of cervical cancer in the United States has been gradually declining as a result of widespread screening, outcomes still remain poor for many with cervical cancer. In addition there has been a negligible survival improvement over the past decade. [2] Even with the increased screening in the U.S., 48% of patients still present at an advanced stage [2]. Globally cervical cancer is widespread (no. 3 cancer in women) and lethal (with a mortality incidence ratio of 52%) [3]. Several prospective randomized trials compared concurrent chemotherapy and radiation to radiation alone for advanced cervical cancer and showed substantial improvement in local control and overall survival in the late nineties [4, 5]. As a result, the National Cancer Institute issued a treatment alert in 1999 establishing chemoradiation as the standard of care for advanced cervical cancer. Radiotherapy for cervical cancer currently consists of radiation in the form of external beam delivered over 5-6 weeks of daily therapy followed by or interdigitated with intracavitary or less frequently, interstitial brachytherapy. These procedures remain invasive and require use of supportive medications ranging from general anesthesia in the operating room to a combination of sedatives and narcotics for insertion of the brachytherapy devices. Furthermore, intracavitary brachytherapy delivers dose to a limited volume of tissue around the cervix and may be inadequate for delivering dose to tumors that extend to the pelvic sidewall. As a result, even with the use of chemoradiation, approximately 30% of patients with locally advanced disease will have a locoregional recurrence [5]. These results of best local control for Stage III-IVA cervix cancer of 70% applies to carefully chosen patients in clinical trials. Patients with bulky advanced cervical cancers like the vast majority of patients we see at Parkland (PMH) and UTSW have an inferior local control which is hampered by poor performance status of these patients. In a recent review of patients from 2003-2011 at PMH, the actuarial overall survival for all II-IVa pts was only 34% at 5 years [6]. A significant group of patients had locoregional failure or persistence, presumably due to bulky tumor volume exceeding the limitations of available radiation and chemotherapeutic modalities. Additionally, patients often present with multiple untreated co-morbidities which makes them often unable to undergo standard chemoradiation and brachytherapy often compromising the delivery of adequate radiation dose and hence the tumor local control. Furthermore, current treatments are often unpalatable for many patients because they are either too invasive, inconvenient or inadequate.

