
The implementation of Intracavitary brachytherapy (which is the most commonly applied form of Brachytherapy in the US) [7] in bulky tumors (esp. Stage IIIB tumors which extend to the pelvic side-wall), results in inadequate dosage to tumor especially at side-wall of pelvis. This occurs because of the rapid falloff of radiation dose from intracavitary brachytherapy sources which may explain the relatively high rate of local failure in bulky stage III cervical cancers.

More advanced methods of delivery are available, like Image Based high dose rate Brachytherapy with the Europeans being the innovators in this area. Under the aegis of the GEC-ESTRO group many new frameworks for HDR Cervix brachytherapy have been introduced with emphasis on volumetric assessment of dose to cervix CTV recommended to be based on MR imaging [8]. The most updated French Multicentric experience of over 600 patients with cervical cancer comparing 2D with 3D image based intracavitary brachytherapy

showed that in the advanced cervical cancer patients (mostly stage II; as IIIB were only 25% of group) local recurrence was still 25%. They did not break up recurrence by stage.[9]

For the bulkier tumors, in order to improve tumor control, interstitial brachytherapy is recommended by some. These are more invasive procedures and involve transperineal Interstitial needle placement into cervix tumor with General anesthesia, hospital inpatient stay, extensive support and involvement of considerable resources and provider-hours. Even with these invasive procedures, the best results provide 60-65% local control at 2-3 years for all stages [10, 11]. This is an important problem, since locally advanced cervical cancer continues to recur despite current treatments and more effective, less toxic and more convenient treatments are necessary.

The Vienna group has pioneered a combined Intracavitary- Interstitial technique which requires Intra-operative MRI suite which is impractical in the US setting and particularly in the county hospital setting which we work in.[12]

Their best results with IIIB disease are using 3D image based hybrid version of Intracavitary/interstitial brachytherapy using a customized ring applicator with needles achieved a local control of 86% for IIIB cancer .[13]This process is very resource intensive and requires interstitial MR guided-Brachytherapy expertise which may not be available in most US centers.

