2. STUDY OBJECTIVES

2.1 Primary Objective

The primary objective is to improve primary tumor local control of eligible LACC using Image Guided Hypofractionated Radiation Treatment as the mechanism for delivering boost therapy to 85% at 2 years post treatment.

A phase I safety lead-in will be performed as described in section 8.

For the safety lead-in phase, acute grade ≥ 3 gastrointestinal (GI) toxicity (perforation, obstruction, bleeding, ulceration, necrosis, proctitis and diarrhea requiring elective or urgent hospitalization) and grade ≥ 3 genitourinary (GU) toxicity (cystitis, hematuria and incontinence requiring elective or urgent hospitalization) within 90 days from the commencement of Image

Guided Hypofractionated Radiation Treatment boost will be assessed. Toxicity will be graded according to the Common Terminology Criteria for Adverse Events (CTCAE) version 4.

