4.8.2 Dosimetry and Treatment volumes

Treatment volumes (CTVCxHR) will be modeled after those published in GEC-ESTRO brachytherapy guidelines (High risk Cervix CTV)[34]. In addition 2 cm of the full thickness of uterine canal length from the external os or proximal end of tumor (whichever is superior) will be included in the CTVCXHR and targeted to prescription dose with Image Guided Hypofractionated Radiation Treatment .However the extension of tumor beyond cervix which will be covered by dose may result in a larger and more irregular base to the “pear”. Depending upon the extent of uterine canal extension of the tumor; we will cover the length of the uterine canal with the 2 cm longitudinal margin or greater if necessary (depending upon tumor extent) from the center of the uterine canal An additional 0.3-0.5 cm in the axial plane and 0.5cm in the longitudinal plane (cranio-caudal) will be added to the CTV to constitute the planning treatment volume (PTV) depending on the institution’s accuracy and treating physician’s preference.

Three-dimensional coplanar or non-coplanar Intensity Modulated Radiotherapy (IMRT) beam arrangements will be custom designed for each case to deliver highly conformal prescription dose distributions. Non-opposing, non-coplanar beams are preferable. Typically, 7-15 beams of radiation will be used with roughly equal weighting. Generally, more beams are used for larger lesion sizes. For this protocol, the isocenter is defined as the common point of gantry and couch rotation for the treatment unit. Field aperture size and shape should correspond nearly identically to the projection of the PTV along a beam’s eye view (i.e. no additional “margin” for dose build up at the edges of the blocks or MLC jaws beyond the PTV). As such, prescription lines covering the PTV will typically be the 70-90% line (rather than 95-100%); however, higher isodoses (hotspots) must be manipulated to occur within the target and not in adjacent normal tissue and dose heterogeneity is expected. The isocenter in stereotactic coordinates will be determined from system fiducials (or directly from the tumor) and translated to the treatment record.

The treatment dose plan will be made up of multiple beams. The prescription dose in 4 fractions will be delivered to the margin of the PTV and fulfill the requirements below.

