7.1.2 Disease Parameters

Measurable disease: Measurable lesions are defined as those that can be accurately measured in at least one dimension (longest diameter to be recorded) as ≥ 20 mm with conventional techniques (CT, MRI, x-ray) or as ≥ 10 mm with spiral CT scan. All tumor measurements must be recorded in millimeters (or decimal fractions of centimeters).

Note: Previously irradiated lesions are non-measurable except in cases of documented progression of the lesion since the completion of radiation therapy.

Non-measurable disease: Will be evaluated clinically. The response will be recorded based on the clinical digital exam.

Target lesion: For purposes of this study the cervical tumor is the target lesion, longest diameter (LD) will be measured from T2W MR study if available or contrast CT scan. The baseline LD will be used as reference by which to characterize the objective tumor response.

Non-target lesions: All other lesions (or sites of disease) including any measurable lesions over and above the 6 target lesions should be identified as **non-target lesions** and should also be recorded at baseline. Measurements of these lesions are not required, but the presence or absence of each should be noted throughout follow-up.

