8.3 Sample Size

8.3.1 Overview

Six patients will be used for a safety lead-in stage in this phase II clinical trial. In Standard Phase 1 3+3 clinical trials, there is 0 or 1 DLT out of 6 patients at the MTD, which will be used for a subsequent phase II clinical trials. [36] Prior studies have shown the rate of \geq grade 3 GI toxicity to be 7-14% and 2-5% for \geq grade 3 GU toxicity. The treatment will not be considered to be feasible if the rate of acute GI/GU toxicity is $>30\%$. In this phase II clinical trial, six patients will be used in a safety lead-in stage. If there is 0 or 1 DLT out of 6 patients at the safety lead-in stage, we will proceed to a phase II clinical trial. Otherwise, we will stop the trial, and will not proceed to a phase II trial with a given dose.

The primary goal of this study is to assess the 2 year pelvic local control (excluding nodes) from cervix cancer. Historical data shows that the 2 yr-pelvic local control rate is approximately 65%. [4, 5, 9] We expect that this will be increased to 85% with the treatment of cervix Image Guided Hypofractionated Radiation Treatment boost based on best results with Intracavitary/interstitial data [13]. We assume that the loco regional recurrence-free survival follows an exponential distribution. Accrual to the study is assumed to be uniformly distributed over time with no loss to follow-up. Twenty-one patients will achieve 80% power in detecting the difference between the null hypothesis of 2-year recurrence-free survival rate of 65% and the alternative hypothesis of 2-year recurrence-free survival rate of 85% at a two-sided 0.1 significance level assuming a 2-year accrual period and 2-year follow-up period. It is expected that 21 patients will be recruited in 2 years with an expected accrual rate of 10-11 patients per year.

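### The primary-endpoint event has no single site definition: section 7.1.6 says cervix, 8.3.1 says pelvis without nodes and then loco-regional, and 8.5.1 leaves its terms undefined.

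*Combined protocol and SAP*

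**What the plan says.** The protocol describes the primary-endpoint event in several places and in different words.

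- **Section 2.1:** "The primary objective is to improve primary tumor local control of eligible LACC", with a target of 85% at 2 years.
- **Section 7.1.6** (under the progression-free survival heading), the only rule that sorts progression by site: "Local tumor (cervix-which is primary endpoint) , Regional(pelvic nodal) and distant (Paraortic and visceral organ)metastases".
- **Section 8.3.1, goal:** "The primary goal of this study is to assess the 2 year pelvic local control (excluding nodes) from cervix cancer".
- **Section 8.3.1, same paragraph, statistical model:** "We assume that the loco regional recurrence-free survival follows an exponential distribution". The hypotheses that follow are stated for 2-year recurrence-free survival.
- **Section 8.5.1:** annual reports give a pelvic control rate, Kaplan-Meier is applied to time to local failure, and the one-sample log-rank test is applied to local recurrence-free survival. None of the three terms is defined.

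Two other places bear on what counts as local. Section 7.1.2 says: "For purposes of this study the cervical tumor is the target lesion". Section 4.8.2, on the boost volume, says: "the extension of tumor beyond cervix which will be covered by dose may result in a larger and more irregular base".

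**The concern.** This is a single-arm test of 21 patients against a fixed 65%. Such a test means something only if the event counted in the trial is the event behind the benchmark. Here the event depends on which section the person scoring failures follows.

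The undefined zone is close to the question the trial asks. Section 1.1 argues that intracavitary brachytherapy "may be inadequate for delivering dose to tumors that extend to the pelvic sidewall", and that in bulky tumors its use "results in inadequate dosage to tumor especially at side-wall of pelvis". Stages IIIA (lower third of the vagina) and IIIB (pelvic wall) are eligible. Failures outside the cervix but inside the pelvis are therefore informative about the boost, and 7.1.6 gives a separate one no site.

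If the definition is settled only after failures are known, the choice of wording could decide a result in so small a trial.

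**Working it through.** **1. The definitions applied to one event.** Take a non-nodal soft-tissue recurrence in the pelvis, separate from the cervical tumor.

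| Section | Wording in brief | Does the event count? |
|---|---|---|
| 2.1 | primary tumor control | unclear |
| 7.1.6 | cervix / pelvic nodes / para-aortic and visceral | no category |
| 8.3.1, goal | pelvis without nodes | yes |
| 8.3.1, model | loco-regional | yes, and on its usual meaning nodal failure too |
| 8.5.1, report | pelvic control | yes, if pelvic has its plain meaning |
| 8.5.1, analysis and test | local failure, local recurrence | undefined |

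The response criteria do not close the gap. Under 7.1.4 a new lesion is progressive disease, so the event is recorded as progression, but 7.1.6 supplies no site label for it. The two descriptions in 8.3.1 also disagree with each other: one excludes nodes and the other, as usually understood, includes them.

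**2. The planned sample size.** Inputs from 8.3.1: 65% against 85% at 2 years, exponential model, two-sided 0.10, 80% power, 2 years of uniform accrual plus 2 years of follow-up, no loss.

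- Hazards: −ln(0.65)/2 = 0.2154 and −ln(0.85)/2 = 0.0813 per year; ratio 0.377.
- Probability of an event under the alternative, v1 = 0.215. Expected null cumulative hazard per patient under the alternative, v0 = 0.215 × 0.2154/0.0813 = 0.571.
- n = [(1.645·√v0 + 0.842·√v1)/(v0 − v1)]² = 21.1.

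This agrees with the stated 21 to within rounding. Simulated power of the one-sample log-rank test at n = 21 is about 77%. The arithmetic does not depend on the site definition. What depends on it is which events enter the test.

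**3. Weight of one event.** The step from 65% to 85% is 0.20 × 21 = 4.2 patients. One failure left out moves the crude 2-year rate by 1/21 = 4.8 points. At 85% control only 0.15 × 21 = 3.15 failures by 2 years are expected in total.

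**4. Sensitivity.** The documents give no split of failures by site, so the numbers of omitted or added failures here are assumptions. The test is the planned one-sample log-rank at n = 21.

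- *True pelvic control equals the null 65%, but some failures are not scored.* The chance of declaring improvement is about 4% with none omitted. It is about 10%, 25% or 47% if the equivalent of 1, 2 or 3 of 21 failures by 2 years is omitted (scored rates 69.8%, 74.5% and 79.3%).
- *85% holds for the cervix alone, and the pelvic definition is scored.* If a further 3, 5 or 10 percentage points of patients fail elsewhere in the pelvis outside nodes, power falls from about 77% to about 62%, 51% or 26%.

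Both sets show how sensitive the test is to the definition. Neither is a forecast.

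**The case against.** The strongest reply is that local tumor in 7.1.6 means the cervical cancer, not the cervix as an organ. Section 2.1 speaks of the primary tumor, 7.1.2 makes the cervical tumor the target lesion, 7.1.4.2 names only nodes as non-target lesions, and the boost in 4.8.2 covers extension beyond the cervix. On that reading regrowth at the side wall in a IIIB patient, or in the lower vagina in a IIIA patient, is failure of the primary tumor and is already local. This stands for contiguous disease. It does not clearly cover a separate deposit, and the documents do not state it.

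A reader might infer that a patient with side-wall recurrence is scored as controlled under 7.1.6. The text does not say so: a separate recurrence there is unclassified, and it still counts as progression.

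A reader might also infer that the plan is biased toward success by a known amount, for example 3/21 = 14.3 points, or 71% of the 20-point effect. The documents do not support this either. Section 1.1 presents the same rise from 65% to 85% simply as local control. It also reports the study behind the 85% as local control in IIIB disease, and cites one of the sources for the 65% for locoregional recurrence. Which sites those benchmarks counted cannot be settled from the documents. Three omitted failures would be nearly all of the 3.15 expected at 85%. Section 8.5.1 also reports pelvic control, so a cervix-only count would require following a narrow reading of 7.1.6 over section 8.

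**Conclusion.** The inconsistency is real and should be corrected. Section 7.1.6, the two statements in 8.3.1 and the undefined terms in 8.5.1 do not identify one event, and a separate non-nodal pelvic recurrence is a failure in one place and unassigned in another.

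The direction of bias is conditional. If 7.1.6 is applied as cervix only, and the 65% is pelvic control as 8.3.1 says, omissions can only favour success, at 4.8 crude points per omitted failure. The total shift is unknown. The planned Kaplan-Meier and log-rank analysis would also not move by exactly the crude amount. The sample size stands.

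**What to change.** In 7.1.6, define local failure (the primary endpoint) as any non-nodal pelvic failure, including cervix, uterus, vagina, parametria and pelvic side-wall soft tissue. This follows the goal already stated in 8.3.1. In addition:

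- State whether direct bladder or rectal involvement is local or falls under visceral organ. Stage IVA is eligible, so the case can arise.
- Use the one definition and one term in 2.1, 7.1.6, 8.3.1 and 8.5.1.
- In 8.3.1, replace the loco-regional term in the exponential assumption with the same term.
- Make the change before failures are scored.

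A descriptive table of failures inside and outside the boost volume would be useful but is optional.

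The cost is a short amendment to wording. No treatment, visit or sample size changes. The downside is that observed local control may be lower than under a cervix-only reading.

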7.2 Safety/tolerability

Analyses will be performed for all patients having received all three fractions of *Image Guided Hypofractionated Radiation Treatment*. The study will use the CTCAE version 4.0 for reporting of non-hematologic adverse events (<http://ctep.cancer.gov/reporting/ctc.html>).

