Diagnosis and Main Inclusion Criteria	Inclusion Criteria 
 • Biopsy proven squamous, adenosquamous, or adenocarcinoma of uterine cervix • Willing and capable of consent • FIGO Stage IB2 - IVB, cervical cancer
Study Product(s), Dose, Route, Regimen	Patients enrolled in this study must have received or planned to receive 45Gy of prior external beam radiation therapy. Following completion, patients will receive 28 Gy in 4 fractions using Image Guided Hypofractionated radiation therapy techniques.
Duration of administration	All radiation therapy should be preferably completed within 56 days.
Reference therapy	Image Guided Hypofractionated Radiation Treatment will be compared to standard of care which consists of standard chemoradiation followed by intracavitary high dose rate brachytherapy.

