We propose Precise Image Guided Hypofractionated Radiation treatment building on our experience with prostate cancer which has a similar anatomic profile to bulky cervical cancer albeit involves slightly larger volume of treatment. [14] Brachytherapy is very effective in delivering dose to fixed volume within close proximity cervix, while Image Guided Hypofractionated Radiation Treatment can be shaped to larger patient specific tumor volumes. We will use existing HDR brachytherapy regimens and modified Brachytherapy tumor targets to deliver precise doses of SABR in 4 fractions of 7Gy each delivered over 2-3 weeks.

It is predicted that the dose limiting toxicity from this treatment will likely relate to Grade 4 bladder/urethral dysfunction (e.g., ulceration, bleeding, pain, narrowing and frank stricture) and rectal damage (ulceration, bleeding, chronic inflammation, and pain or fistula) causing emergent and life-threatening situation requiring admission. Based upon the best results of Vienna combined Intracavitary-Interstitial Brachytherapy, we predict that with more complete radiation dose delivery to these tumors using Image Guided Hypofractionated Radiation Treatment, we will be able to increase the local control from 65 to 85%at 2 years. A safety-lead in will be used for the first 6 patients to see if we have any unexpected Grade 3,4 toxicity within first 90 days after commencement of Image Guided Hypofractionated Radiation boost.

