4. RADIATION THERAPY

4.1 Dose Specification

- a. Initial Pelvic (+/- Para-aortic) fractionated external beam Radiation with 45 Gy to combined PTV with a boost to 55Gy for PET positive/CT enlarged nodes;
- b. Image Guided Hypofractionated Radiation Treatment boost to Cervix High risk CTV/PTV 28GY/4 fx.

Patients will receive 4 fractions of 7 Gy each via stereotactic body radiation as boost therapy to a volume that encompasses the cervical tumor. A minimum of 40 hours should separate each treatment.

4.2 Details of Planning for external Beam Pelvic RT:

Daily external beam radiation (with concurrent weekly cisplatin) will be preferably given using intensity modulated radiation therapy (IMRT) to the primary tumor in the cervix and pelvic lymphatics. The para-aortic lymph nodes will also be treated only if there is 18F-FDG uptake on the staging PET/CT scan. The following targets will be outlined.

- Gross tumor volume-node (GTV node): This will be designated by the 18F-FDG avid lymph node as outlined on the PET/CT scan.
- Clinical target volume-nodal (CTV nodal): This volume will be contoured as recommended by Consensus Guidelines For Delineation of Clinical Target Volume for Intensity Modulated Pelvic Radiotherapy in the Definitive Treatment of Cervix Cancer [33]
- Clinical Target Volume Cervix and Parametria (CTV cervix): This volume will be contoured as recommended by Consensus Guidelines For Delineation of Clinical Target Volume for Intensity Modulated Pelvic Radiotherapy in the Definitive Treatment of Cervix Cancer [33]

For pelvic /Para-aortic radiation, dose should preferably be given as follows (All targets will be treated simultaneously, except as noted.):

- The planning target volume-nodal (PTV nodal) (CTV nodal with 7 -mm margin) will receive 45 Gy. Treatment will be delivered once daily, 5 fractions per week. The planning target volume cervix (PTV cervix) (CTV cervix with 7mm margin) inferiorly and superiorly lateral and posterior margin will be 7-10 mm based upon rectal distension.
- The planning target volume gross node (PTV Node Boost) (GTV node+5mm margin) laterally, posteriorly, inferiorly and superiorly; this volume will not extend into bowel will receive 55 Gy in 25 fractions. Treatment will be delivered once daily, 5 fractions per week.

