6.3 Follow-up Procedures

Patients will be followed for 5 years after completion of treatment or until death, whichever occurs first. Patients removed from treatment for unacceptable adverse events will be followed until resolution or stabilization of the adverse event. Patients will be seen at clinic at 1 month, 3 months, 6 months, 12 month, 18 month, 24 month, then annual for 3 more years post-therapy for evaluation of disease progression as well as radiation toxicities.

- For the purposes of this protocol completion of therapy will be considered the day on which the fourth and final fraction of Image Guided Hypofractionated Radiation Treatment is delivered
- Any visit between one month and four month after the completion of therapy will be considered the three months visit
- Any visit between five months and eight months after completion of therapy will be considered the sixth month follow up
- Any visit between ten months and fourteen months after the completion of therapy will be considered the one year follow up
- Follow ups beyond one year can be scheduled \pm 2 month for each time point.

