6.5 Removal of Subjects from Study

Patients can be taken off the study treatment and/or study at any time at their own request, or they may be withdrawn at the discretion of the investigator for safety, behavioral or administrative reasons. The reason(s) for discontinuation will be documented and may include:

- 6.5.1 Patient voluntarily withdraws from treatment.
- 6.5.2 Patient withdraws consent)
- 6.5.3 Patient is unable to comply with protocol requirements
- 6.5.4 Patient demonstrates disease progression (unless continued treatment with study drug is deemed appropriate at the discretion of the investigator).
- 6.5.5 Patient experiences toxicity that makes continuation in the protocol unsafe.
- 6.5.6 Treating physician judges continuation on the study would not be in the patient's best interest.
- 6.5.7 Patient becomes pregnant during active treatment (pregnancy to be reported along same timelines as a serious adverse event).
- 6.5.8 Lost to follow-up. *Example language: If a research subject cannot be located to document survival after a period of 2 years, the subject may be considered "lost to follow-up." All attempts to contact the subject during the two years must be documented and approved by the Data Monitoring Committee.*

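### Section 7.2 ties the safety analyses to completing a number of boost fractions; this conflicts with the treated-patient sets elsewhere and, if followed, could lower the reported acute toxicity rate

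*Combined protocol and SAP*

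**What the plan says.** Section 7.2, the protocol's safety and tolerability section, reads: "Analyses will be performed for all patients having received all three fractions" of the boost.

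The boost is described differently in five other places:
- Study Summary: "patients will receive 28 Gy in 4 fractions using Image Guided Hypofractionated radiation therapy techniques".
- Section 1.1: "deliver precise doses of SABR in 4 fractions of 7Gy each delivered over 2-3 weeks".
- Section 4.1: "Patients will receive 4 fractions of 7 Gy each via stereotactic body radiation as boost therapy".
- Section 4.8.2: "The prescription dose in 4 fractions will be delivered to the margin of the PTV".
- Section 6.3 dates completion of therapy to the day "the fourth and final fraction of Image Guided Hypofractionated Radiation Treatment is delivered".

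Four sections describe the toxicity population without any completion condition. Section 4.12 makes anyone treated on the protocol evaluable for toxicity. Section 7.1.1 makes all patients evaluable from their first radiation treatment. Section 8.5.1 divides the count of patients with grade 3-5 toxicity by the number treated on the protocol, for both the acute and the late rate. Section 10.3 refers to treated patients.

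The plan also foresees early stopping for toxicity. Section 4.12 lists an unacceptable adverse event among the reasons to end treatment before all fractions are given. Section 6.5 lists "Patient experiences toxicity that makes continuation in the protocol unsafe". Section 6.3 adds: "Patients removed from treatment for unacceptable adverse events will be followed until resolution or stabilization of the adverse event".

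**The concern.** There are two defects in one sentence. The first is the fraction count, which disagrees with the rest of the document. The second would survive a corrected count: membership of the safety set depends on how much of the boost the patient received, and that can depend on the outcome being measured. A patient who has a grade 3 or worse GI or GU event during the boost and stops because of it would leave both the numerator and the denominator.

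Acute and late grade 3 or worse GI and GU toxicity is a secondary objective (Section 2.2.1), and the absence of increased acute GI or GU toxicity is part of the study question (Study Summary, Section 8.1.1). With 21 patients, one exclusion is visible in the reported percentage. Two analysts, one following 7.2 and the other 8.5.1, could report different rates from the same data, and each could point to the protocol for support.

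**Working it through.** **Step 1: the fraction count.** Five places give four fractions, and Section 7.2 implies three. If the boost has four fractions, the 7.2 wording could mean every fraction or at least three. Either reading leaves out a patient who stops after one or two.

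**Step 2: can the event cause the exclusion?** For acute toxicity it can. The boost is planned over 2-3 weeks (Section 1.1), and the acute window is 90 days from the start of the boost (Sections 2.1 and 2.2.1). For late toxicity it cannot. The late window opens at about day 90 (Section 2.2.1, from boost start) or day 91 (Section 8.2, from the start of protocol treatment). The Study Summary prefers all radiation to be finished within 56 days, so on that schedule the boost is over before a late event is counted, whichever anchor is used.

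**Step 3: direction.** Let s be the share of treated patients who stop early, and let p_c and p_s be the event rates in completers and stoppers. Then

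completers' rate − treated rate = s × (p_c − p_s).

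The difference is negative when stoppers have the higher event rate, as happens when the event is the reason for stopping. It is positive when they have the lower rate, and zero when s = 0. For late toxicity, and for stopping for other reasons, the sign depends only on how p_s compares with p_c.

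**Step 4: size, for illustration only.** The plan states no figure to reproduce here. Inputs:
- 21 patients (Section 8.3.1).
- Prior grade 3 or worse rates of 7-14% (GI) and 2-5% (GU), also from Section 8.3.1. That section does not label them as acute; applying them to the acute rate is an assumption.
- Combined rate: 7-14% if GI and GU events fall in the same patients, 7+2 = 9% to 14+5 = 19% if they never do.
- Expected patients with an event: 21 × 0.07 = 1.47 to 21 × 0.19 = 3.99.
- Number of early stoppers: not in the documents. One is assumed.

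Intervals are exact binomial, the method named in Section 8.5.1.

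| Treated set | One stopper with an event dropped | Shift (points) |
|---|---|---|
| 2/21 = 9.5% (1.2 to 30.4%) | 1/20 = 5.0% (0.1 to 24.9%) | −4.5 |
| 3/21 = 14.3% (3.0 to 36.3%) | 2/20 = 10.0% (1.2 to 31.7%) | −4.3 |
| 4/21 = 19.0% (5.4 to 41.9%) | 3/20 = 15.0% (3.2 to 37.9%) | −4.0 |

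Check of the middle row with the formula: (1/21) × (0.10 − 1) = −0.043. If the dropped stopper had no event, 3/21 becomes 3/20 = 15.0%, a rise of 0.7 points: (1/21) × (0.15 − 0) = 0.007.

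The interval for 3/21 is 36.3 − 3.0 = 33.3 points wide, so the shift is small beside the sampling uncertainty.

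**The case against.** The strongest reply is that Section 8.5.1 already settles the matter. It sits in the analysis plan and gives a numerator, a treated-patient denominator and an interval method for the acute and late rates. Section 7.2 names none of these. An analyst may well follow 8.5.1, and Sections 4.12, 7.1.1 and 10.3 lean the same way. The 7.2 sentence may also be a leftover: 8.5.1 mentions lung cancer subscales, 7.1.2 refers to six target lesions although the cervical tumor is the target lesion, and 6.5 still carries example language. Both points are fair, and they keep the concern at what could happen if 7.2 is followed. They do not remove it, because no section ranks 7.2 against 8.5.1.

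A second reply is that few patients could be affected. Only an event before the last fraction can stop the boost. If events were spread evenly over the 90 days (an assumption; the timing is unknown), the expected number during the boost would be between 1.47 × 14/90 = 0.2 and 3.99 × 21/90 = 0.9 patients, and not all of those would stop. This stands, and it is why only a one-patient exclusion is shown. Section 6.3 also keeps following patients removed for adverse events, so the issue is who is counted in the analysis; event collection continues.

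A reader might infer that 7.2 also weakens the safety lead-in, the 30% limits or the first-nine and first-fifteen rule. The documents do not support that. Section 10.3 uses treated patients, its counts carry no completion condition, and nothing shows that 7.2 governs any of these decisions.

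**Conclusion.** The point holds as a conflict in the text that should be fixed. Section 7.2 disagrees with the rest of the document on the number of fractions, and its set conflicts with the treated-patient wording in 4.12, 7.1.1 and 8.5.1. It also differs from the wording in 10.3, with no effect on the decision rules claimed.

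If 7.2 is followed and a patient stops the boost because of an acute grade 3 or worse GI or GU event, the reported acute rate falls. The illustrated fall is about 4 to 4.5 points per such patient, for 2 to 4 events in 21. This rests on an assumed number of stoppers and on prior rates not labelled as acute. The shift is smaller than the interval width, and it is zero if nobody stops early.

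A reader might infer a proven or material bias, or a downward bias in late toxicity as well. Neither is supported: no non-completion rate is given, and for late toxicity the sign is open. The text conflict is certain; its practical effect is not.

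**What to change.** Reconcile the fraction count in 7.2 with the Study Summary and Sections 1.1, 4.1, 4.8.2 and 6.3. Replace the sentence on the analysis set in 7.2 with one that does not depend on the count:

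*Safety analyses will include all patients who receive at least one fraction of the Image Guided Hypofractionated Radiation Treatment boost, whether or not they complete it.*

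State that this set is the treated-patient denominator for the acute and late rates in 8.5.1, which Section 2.2.1 anchors to the start of the boost, and that it is also the set for 8.5.2. Report how many patients did not complete the boost, with reasons.

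Leave the rule in 4.12 and 7.1.1 as it is, so that patients remain evaluable for toxicity from their first radiation. The Study Summary admits patients whose pelvic course is still only planned. Toxicity in someone who enrolls then and never reaches the boost should still be reported, separately from the boost rates.

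The cost is one replaced sentence and short additions to 8.5.1 and 8.5.2, with no new data and no extra patients. The downside is that the reported toxicity rate may be slightly less favourable.
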